3. STUDY DESIGN

3.1. Overall Study Design and Flow Chart

This study will be an open label, randomized, three-arm, parallel group, single dose, study in healthy participants (males and females), performed at multiple study centers.

A total of 207 evaluable healthy male and female participants will be randomized in a 1:1:1 ratio between the three treatment groups (69 participants per group). Each participant will receive AZD7442 as either a single IM dose (co-formulation; AZD8895 + AZD1061) from a single vial or as two separate IM doses of the individual mAbs (AZD8895 and then AZD1061) from two separate vials from either clonal cell line material or cell pool material as follows:

- **Treatment A:** 300 mg (total protein) AZD7442 as a single IM dose (co-formulation of 150 mg AZD8895 + 150 mg AZD1061) (clonal cell line material).
- **Treatment B:** 300 mg (total protein) AZD7442 as two separate IM doses of the individual mAbs (150 mg AZD8895 and then 150 mg AZD1061) (clonal cell line material).
- **Treatment C:** 300 mg (total protein) AZD7442 as two separate IM doses of the individual mAbs (150 mg AZD8895 and then 150 mg AZD1061) (cell pool material).

The product in Treatment Groups A and B is derived from material that originated from a clonal cell line, with a separate cell line, GMP cell bank, and manufacturing process for AZD8895 and AZD1061. The product in Treatment Group C is derived from material that originated from a non-clonal cell pool, with a separate pool of cells, GMP cell bank, and manufacturing process for AZD8895 and AZD1061. The clonal cell line is derived from a subpopulation of the respective cell pool, and there are no differences in antibody sequence between these cell banks. These materials have been demonstrated to be analytically comparable to each other. Refer to [Table 5-1](#) for details on the IMP.

Additionally, within each of the treatment groups, participants will be randomized 1:1:1 to one of the three injection sites:

- Lateral thigh,
- Gluteal dorsal,
- Gluteal ventral.

Further, participants will be stratified based on the body weight and vaccination status at randomization as follows:

[figure not shown]
- Body weight at randomization: < 70 kg; 70 to < 80 kg; and \geq 80 kg
- Anti-SARS-CoV-2 vaccination status at randomization: non-vaccinated or vaccinated (with one or more locally approved/authorized COVID-19 vaccine doses)

The study will comprise of:

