- A Screening Period of up to 28 days that requires participants to visit the Clinical Unit (Visit 1).
- A Treatment Period of 1 day (Day 1; Visit 2) during which participants will be admitted to the study Clinical Unit and be randomized to receive their dose of IMP (AZD7442 as either a single IM dose or two separate IM doses). Participants will stay at the study clinic for at least 8 hours after dosing and will be discharged from the Clinical Unit at the discretion of the investigator, on the same day.
- A Follow-up Period of approximately 1 year consisting of regular visits to the study Clinical Unit starting from the day after dosing, Day 2 through to Day 361. The subsequent study visits total in 11 outpatient follow-up visits (Visits 3 to 13).

Details of IMP administration are provided in Section [5.4.6](#).

Figure 3-1 Study Flow Chart

Abbreviation: IM: Intramuscular

Treatment A: 300 mg IM coformulation in one injection of 2 mL (clonal cell line material)

Treatment B: 300 mg IM from individual vials, 2 injections of 1.5 mL (clonal cell line material)

Treatment C: 300 mg IM from individual vials, 2 injections of 1.5 mL (cell pool material)

Table 3-1 Schedule of Assessments: Screening, Randomization, and IMP Administration

Procedures	Screening Period		Treatment Period	
	Day -28-to -1			
	Visit 1	Visit 2		
Written informed consent and assignment of enrollment code	X			
Medical history	X		X ^a	
Demographics	X			
Full physical examination, height, weight, and BMI	X		X ^a	
12-Lead ECG	X		X	
Vital signs	X		X	
Serum chemistry ^b	X		X	
Hematology ^b	X		X	
Coagulation ^b	X		X	
Urinalysis ^b	X		X	
FSH (postmenopausal women only) ^{b,c}	X			
Pregnancy test (serum β-hCG) ^c	X			
Pregnancy test (urine dipstick) ^{c,d}			X	
HIV, hepatitis B, hepatitis C testing	X			
Urine drug and alcohol screen ^{b,e}	X		X	
Assessment of AEs/SAEs ^f	X		X	
Concomitant medications	X		X	
Verify eligibility criteria	X		X	
Anti-COVID-19 vaccination status ^g	X		X	
Monitoring for COVID-19 symptoms and exposure history	X		X	
Documented SARS-CoV-2 RT-PCR test taken ≤ 3 days before Day 1 OR Rapid SARS-CoV-2 antigen test (for screening criteria) ^h			X	
SARS-CoV-2 serology ⁱ			X	
Randomization			X	
Participant identification card			X	
AZD7442 administration ^j			X	
Injection site monitoring			X	

Procedures	Screening Period	Treatment Period
Study Day	Day -28-to -1	Day 1
Study Visit	Visit 1	Visit 2
Serum sample for AZD7442 PK ^k		X
Serum sample for anti-AZD7442 antibodies ^l		X

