5.4.6.2. Treatment B: AZD8895 and AZD1061 Clonal Cell Line Material in Separate Vials

AZD7442 must be administered as separate injections to the participant in sequential order, with no participant receiving a dose of AZD8895 without also receiving the matching dose of AZD1061.

Obtain one vial each of AZD8895 and AZD1061 clonal cell line material for administration and equilibrate to room temperature prior to use.

Accurately withdraw 1.5 mL of AZD8895 into an appropriately sized syringe. Accurately withdraw 1.5 mL of AZD1061 into a separate appropriately sized syringe.

Administer the injections of AZD7442 (AZD8895 and AZD1061) with an appropriate needle according to standard procedures for IM injections in the appropriate region (lateral thigh, gluteal dorsal, or gluteal ventral). AZD8895 must be administered first in the appropriate region followed by AZD1061 in the second region on the opposite side.

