11. STATISTICAL METHODS AND SAMPLE SIZE DETERMINATION

11.1. Description of Analysis Sets

11.1.1. General Principles

A separate SAP will be compiled for this study. The details of the formal hypothesis testing will be detailed in the SAP.

Regarding PK comparability, if the 90% CIs for the geometric mean ratios for both AUCinf (AUClast for some agencies) and Cmax are entirely contained within 0.8000 and 1.2500 for all comparisons according to the study objectives, it may be concluded that the 2 formulations (the co-formulation and the formulation from the individual vials) are comparable and the 2 materials (clonal cell line material and cell pool material) are comparable.

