4.10.4 Primary Endpoint

The primary endpoints for evaluation of pharmacokinetic comparability will be assessed using a linear fixed effects analysis of variance model with the natural logarithm of primary PK parameters (eg, AUCinf [for final analysis only], AUClast, Cmax and AUC0-91d [for IA only]) for the individual mAbs AZD8895 and AZD1061, as well as for the sum of the individual mAbs of AZD7442 (AZD8895 + AZD1061) as the response variables, treatment, injection site, anti-COVID-19 vaccination status (as reported on the CRF), and continuous baseline body weight on the log scale as fixed effects and participant as a random effect.

Transformed back from the logarithmic scale, geometric least square means (GLSM) together with CIs (2-sided 95%) will be estimated and presented by treatment. Also, ratios of geometric least square means together with CIs (2-sided 90%) will be estimated and presented.

The following treatment comparisons will apply:

- Treatment A vs Treatment B
- Treatment A vs Treatment C
- Treatment B vs Treatment C

where:

- Treatment A: 300 mg (total protein) AZD7442 as a single IM dose (co-formulation of 150 mg AZD8895 + 150 mg AZD1061) (clonal cell line material).

- Treatment B: 300 mg (total protein) AZD7442 as two separate IM doses of the individual mAbs (150 mg AZD8895 and then 150 mg AZD1061) (clonal cell line material).
- Treatment C: 300 mg (total protein) AZD7442 as two separate IM doses of the individual mAbs (150 mg AZD8895 and then 150 mg AZD1061) (cell pool material).

One statistical model will be fitted for each PK parameter, including all study data. Estimating parameters for the comparisons listed above will be done from this one model making use of the appropriate contrasts.

A variance component covariance structure will be used for the within-participant errors. Degrees of freedom will be determined using Kenward-Roger approximation.

If the estimating algorithms do not converge, these covariance structures will be tried: first-order autoregressive, compound symmetry, unstructured and Toeplitz.

Missing values will not be imputed. In this analysis it is thus assumed that any missing values are missing at random (MAR).

The following figures, in black and white, will be generated:

Figure	Analysis set	Presented by

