4.12 Determination of Sample Size

Preliminary analysis of PK data from the first-in-human study, D8850C00001, indicated that after an IM dose of IMP (separate AZD8895 and then AZD1061 doses) at a dose of 300 mg total protein, the CV% for Cmax of the individual mAbs, AZD8895 and AZD1061 were 35.6% and 38.5%, respectively, while the CV% for AUCs of both individual mAbs, AZD8895 and AZD1061 were < 36.4%. Therefore, assuming a mean ratio of 1 between comparators, 69 participants per group will provide at least 95% power to demonstrate comparability (90% CI contained within 0.8 and 1.25).

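### The primary model pools one residual variance over all three arms, so if arm variances differ some 90% CIs are modestly too narrow and others too wide

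*SAP*

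**What the plan says.** SAP 4.10.4 (Primary Endpoint) models each log-transformed primary PK parameter on treatment, injection site, vaccination status and log body weight, with participant as a random effect. "One statistical model will be fitted for each PK parameter, including all study data", and the three pairwise comparisons are contrasts from that fit. On the error structure it says: "A variance component covariance structure will be used for the within-participant errors". Degrees of freedom are Kenward-Roger. The fallback structures (autoregressive, compound symmetry, unstructured, Toeplitz) apply only on non-convergence, and none lets the variance differ by arm.

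On reporting, the SAP adds: "Also, ratios of geometric least square means together with CIs (2-sided 90%) will be estimated and presented". Under Protocol 11.1.1, comparability may be concluded if the intervals for AUC and Cmax "are entirely contained within 0.8000 and 1.2500 for all comparisons according to the study objectives".

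The nearest safeguard is Protocol 11.2.1, which promises documented review of modeling assumptions but names no test and no remedy for unequal variances. The sensitivity and subgroup analyses in SAP 4.14 concern two audited sites and subgroups, not the variance structure.

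**The concern.** Each participant yields one value per parameter and analyte. Participant variance and residual variance therefore cannot be separated, and the fit reduces to an ANCOVA with one error variance pooled over A, B and C. The third arm's variability then helps set the CI width of a comparison it is not part of.

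The documents do not establish that the variances are equal. Treatment A is one 2 mL injection of a co-formulation in an arginine buffer. B and C are two 1.5 mL injections in a sucrose buffer (Protocol Table 5-1), given on opposite sides: "AZD8895 must be administered first in the appropriate region followed by AZD1061 in the second region on the opposite side". The CVs behind the sample size come from separate injections only (Protocol 11.4), so the documents give none for the co-formulation.

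At stake is the calibration of the 90% CI, since its position relative to 0.80 and 1.25 is the decision criterion.

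**Working it through.** **Inputs from the documents.** 69 per arm, 1:1:1; limits 0.80 to 1.25, or ±0.2231 on the log scale; two-sided 90% CIs. CVs in Protocol Table 11-1: Cmax 35.6% and 38.5%, AUClast 29.1% and 30.4%, AUCinf 26.8% and 36.4%.

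**Assumptions.** CV maps to log-scale variance as v = ln(1 + CV²). Arm CVs are not in the documents, so I borrow the spread across parameters in Table 11-1 (26.8% to 38.5%) as a possible spread between arms. No covariate gain; all 69 per arm are evaluable.

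**The plan's own figure.** SAP 4.12 claims: "assuming a mean ratio of 1 between comparators, 69 participants per group will provide at least 95% power to demonstrate comparability". Approximate power is 2Φ(0.2231/SE − 1.645) − 1 with SE = √(2v/69).
- CV 35.6%: log SD 0.3454, SE 0.0588, power 96.8% (exact 96.7%).
- CV 36.4%: exact 96.0%.
- CV 38.5%: log SD 0.3718, SE 0.0633, power 94.0% (exact 93.8%).

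The claim is reproduced to within about a point. At the largest CV, a strict 95% needs 73 per group.

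**Effect of pooling.** With equal n the model uses 2v̄/n for every contrast, where v̄ is the mean of the three arm variances. The true variance for arms i and j is (vᵢ + vⱼ)/n. With k the omitted arm, the ratio of model SE to true SE is

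r = √[2v̄/(vᵢ + vⱼ)] = √[(2/3)(1 + vₖ/(vᵢ + vⱼ))].

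The CI is too narrow exactly when the omitted arm's variance is below v̄, and too wide when it is above. If the variances differ at all, at least one arm lies on each side of v̄, so at least one contrast errs in each direction.

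**Numbers.** v = 0.0694 at CV 26.8% and 0.1382 at 38.5%. From the formula, r is most extreme at the corners of the range:
- A 26.8%, B and C 38.5%, contrast B-C: √[(2/3)(1 + 0.0694/0.2764)] = 0.913.
- A 38.5%, B and C 26.8%, contrast B-C: √[(2/3)(1 + 0.1382/0.1388)] = 1.154.

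One-sided error is roughly 1 − Φ(1.652r), where 1.652 is the t quantile on 204 df. Simulation (1,000,000 trials per row, no covariates) confirms it:

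| CVs A / B / C | Contrast | r | 1 − Φ(1.652r) | Simulated error | Coverage |
|---|---|---|---|---|---|
| 38.5 / 38.5 / 38.5 | each | 1.000 | 4.9% | 5.0% | 90.0% |
| 26.8 / 38.5 / 38.5 | B-C | 0.913 | 6.6% | 6.7% | 86.7% |
| 26.8 / 38.5 / 38.5 | A-B, A-C | 1.054 | 4.1% | 4.2% | 91.7% |
| 38.5 / 26.8 / 26.8 | A-B, A-C | 0.943 | 6.0% | 6.1% | 87.9% |
| 38.5 / 26.8 / 26.8 | B-C | 1.154 | 2.8% | 2.9% | 94.1% |

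With arm-specific variances and Satterthwaite df, every row returns to about 5% and 90%. For the second row, at an observed ratio of 1, the B-C interval is 0.909 to 1.100 pooled and 0.901 to 1.111 arm-specific.

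**Joint rule.** False acceptance for one parameter when all three CIs must lie within the limits:

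| CVs A / B / C | True placement | Pooled | Arm-specific |
|---|---|---|---|
| 26.8 / 38.5 / 38.5 | B-C at limit, A midway | 6.0% | 4.7% |
| 38.5 / 26.8 / 26.8 | A-B at limit, C midway | 5.6% | 4.7% |
| 30 / 38.5 / 38.5 | B-C at limit, A midway | 5.5% | 4.5% |
| 26.8 / 38.5 / 38.5 | A-B at limit, C midway | 3.4% | 4.0% |
| 38.5 / 26.8 / 26.8 | A at limit, B = C | 2.3% | 1.8% |

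Requiring AUC and Cmax together lowers these further.

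**The case against.** The strongest reply is that nothing shows the arms differ. Dose and route are common to all arms, and the protocol describes the materials as analytically comparable with identical antibody sequences. That stands: the concern is conditional.

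The depot argument (shared injection variability in A, averaged over two injections in B and C) is also limited. It applies only to the AZD7442 sum, three of the nine analyte-by-parameter models; for either mAb alone, every participant receives it in one injection. Even for the sum it is weak. If a fraction f of log variance is injection-to-injection, B and C have about (1 − f/2) times A's variance. With f = 0.25, r for A-B is √[(2/3)(1 + 0.875/1.875)] = 0.989; with f = 0.5 it is √[(2/3)(1 + 0.75/1.75)] = 0.976. The resulting errors are about 5.2% and 5.4%.

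Differences would be visible, since SAP 4.10.1 and 4.10.3 plan geometric SD and CV by treatment, and Protocol 11.2.1 allows a different analysis if the planned one proves inappropriate. But those summaries are unadjusted, and choosing the variance model after seeing the data is weaker than naming it in advance.

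The words about one model and all study data are not themselves the problem: a single mean model is compatible with arm-specific variances. The variance-component sentence is the operative one.

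A reader might infer three stronger things. First, that A is known to be more variable; no document says so. Second, that the comparison involving the noisier arm always exceeds 5%; with A the one quieter arm, A-B and A-C each include a noisier arm yet run at 4.2%. Third, that the trial's false-acceptance rate is the per-contrast 6.7%; the all-comparisons rule prevents that.

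**Conclusion.** The plan rests three contrasts on an equal-variance assumption that it neither supports nor relaxes, and equal allocation does not protect against its failure. Under arm CVs assumed to span Table 11-1, SEs are off by −9% to +15%, per-contrast coverage runs from about 87% to 94%, and one-sided error from about 3% to 6.7%. Under the all-comparisons rule the less favourable cases give about 5.5% to 6.0% for one parameter, roughly one point above the arm-specific analysis; other placements stay below 5%. The effect matters only for an interval close to 0.80 or 1.25, and disappears if the variances are equal. This supports a cheap improvement to the model; it does not show that the primary analysis is invalid.

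**What to change.** In SAP 4.10.4:
- Keep the single mean model and the three contrasts.
- Drop the participant random effect. With one value per participant it is not identifiable, and leaving it in beside three residual variances would give four variance parameters for three estimable variances.
- Estimate a separate residual variance per treatment (for example `REPEATED / GROUP=treatment`) with the Kenward-Roger degrees of freedom already named, in all nine models.
- Report the pooled-variance result as a check.
- Reconcile the description of the model as fixed effects with its random participant term, and the reference to within-participant errors with one value per participant.

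At minimum, pre-specify the arm-specific analysis as a sensitivity analysis. If the database is already locked, SAP section 1 provides for an addendum.

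Cost: one model option and a few sentences. If variances are equal at CV 38.5%, power per contrast falls by about 0.1 percentage point (93.8% on pooled df; 93.75% on 136 df), and joint power for one parameter from about 85.2% to 85.0%. If they differ, intervals that pooling made too narrow become slightly wider, as intended, and those it made too wide become narrower.

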4.10.4.1 Methods to minimize bias

This is a controlled open-label study, the sponsor will be blinded to summary outputs until formal database locks occur in order to minimize bias.

4.10.4.2 Adjustment for multiple comparisons

No adjustments for multiple comparisons or multiplicity will be made.

4.10.5 Secondary Endpoints

4.10.5.1 PK Parameters

The following PK parameters will be listed and summarised by means of descriptive statistics:

- Tmax, AUC0-31d, AUC0-61d, tlast, and for final analysis AUC0-91d, AUC0-181d, $t_{1/2}/\lambda_z$, CL/F, and Vz/F
- Diagnostic parameters: λ_z , λ_z lower, λ_z upper, $\lambda_z N$, λ_z span ratio, Rsq adj, AUCextr

4.10.5.2 Immunogenicity

Serum samples for ADA assessments will be conducted utilizing a tiered approach (screen, confirm, titer), and ADA data will be collected at scheduled visits shown in CSP section 3.1. ADA results from each sample will be reported as either positive or negative. If the sample is positive, the ADA titer will be reported as well. In addition, the presence of nAb will be tested for all ADA-positive samples. The nAb results will be reported as positive or negative. A participant is defined as being ADA-positive if a positive ADA result is available at any time, including baseline and all post-baseline measurements; otherwise the participant is defined as ADA negative.

The number and percentage of participants in the following ADA categories in each treatment group will be determined for the individual mAbs AZD8895 and AZD1061, as well as for AZD7442 based on the respective ADA evaluable analysis set (Section 4.5). The number of ADA-evaluable participants in the treatment group will be used as the denominator for percentage calculation.

- ADA positive at any visit (at baseline and/or post-baseline). The percentage of these participants in a population is known as ADA prevalence. For AZD7442, either AZD8895 and/or AZD1061 is ADA positive.
- Treatment-emergent (TE) ADA positive (either treatment-induced ADA positive or treatment-boosted ADA positive). The percentage of these participants in a population is known as ADA incidence. For AZD7442, either AZD8895 and/or AZD1061 is TE ADA positive.
- Non-TE ADA positive, ADA-positive but not fulfilling the conditions for TE ADA-positive.
- Treatment-induced ADA positive:
 - For AZD8895, ADA negative at baseline and ADA positive at ≥ 1 post-baseline assessments with ADA titer ≥ 160 .
 - For AZD1061, ADA negative at baseline and ADA positive at ≥ 1 post-baseline assessments with ADA titer ≥ 80 .
 - For AZD7442, either AZD8895 and/or AZD1061 is treatment-induced ADA positive.
- Treatment-boosted ADA positive (baseline ADA titer that was boosted by ≥ 4 -fold following drug administration). For AZD7442, either AZD8895 and/or AZD1061 is treatment-boosted ADA positive.
- ADA positive post-baseline and positive at baseline.
- ADA positive at baseline and not detected post-baseline.
- TE ADA persistently positive, defined as TE ADA positive participants having at least 2 post-baseline ADA positive measurements with at least 16 weeks (112 days) between the first and last positive measurement, or an ADA positive result at the last available assessment. For AZD7442, either AZD8895 and/or AZD1061 is TE ADA persistently positive.
- TE ADA transiently positive, defined as treatment-emergent ADA positive participants having at least one post-baseline ADA positive measurement and not fulfilling the conditions for TE ADA persistently positive.

To evaluate the ADA responses to AZD7442 in serum the following analyses will be presented:

- A summary of the number and percentage of participants who developed detectable ADA to AZD7442 (ADA results to AZD8895 and AZD1061 will be reported separately) by ADA categories listed above in the different treatment arms will be presented based on the ADA evaluable analysis set. Descriptive statistics of the maximum titer will also be presented by ADA category. ADA results and titers will be summarized by visit and treatment group. ADA results (positive/negative, ADA titer and nAb data for ADA positive samples) will be listed for all participants in the safety analysis set regardless of ADA-evaluable status. AEs in ADA positive participants by ADA positive category will be listed

4.10.5.3 Safety Evaluation

The safety evaluation is presented in the section 4.11 of the SAP.

4.10.6 Exploratory Endpoint

CC1
[REDACTED]

4.11 Safety Evaluation

All safety data (scheduled and unscheduled) will be presented in the data listings sorted by treatment group and participant. Continuous variables will be summarized using descriptive statistics (n, mean, SD, min, median, max) by treatment group. Categorical variables will be summarized in frequency tables (frequency and proportion) treatment group.

The analysis of the safety variables will be based on the safety analysis set.

4.11.1 Extent of Exposure

The IMP administration date and time will be listed for each participant.

4.11.2 Adverse Events

AEs and SAEs will be collected throughout the study from date of informed consent until the end of the follow-up. MedDRA (using the latest or current MedDRA version) will be used to code the AEs.

Adverse events with onset (start date/time) after dosing will be summarized by treatment group (dose level or administration process of AZD7442, Total AZD7442). Tabulations will include causality (related, not related) and severity (mild, moderate and severe). All tabulations will be presented by MedDRA SOC and PT with the exception of the severity tables, which will be presented by PT only. Furthermore, listings of SAE and AEs that led to withdrawal will be made and the number of participants who had any AE, SAEs, and discontinuation events will be summarized. Adverse Events of Special Interest (related to Anaphylaxis and other serious hypersensitivity reactions, and injections site reactions) will be listed and summarized. The AEs that occur before dosing will be excluded from the summary tables.

Adverse events will be listed by each dose of AZD7442. The following information will be included in the listings: verbatim term, MedDRA SOC, PT and lowest level term, start date/time, end date/time, time from last dose, causality, action taken, whether the AE was classified as serious and the outcome.

All tabulations will include the number and percentage of participants.

